8.2.4. Electronic Diary

Prior to vaccination on Day 1, a baseline assessment of fatigue, headache, vomiting, diarrhea, muscle pain, and joint pain will be recorded in the e-diary.

For participants <18 years of age, their parent(s)/legal guardian may complete the e-diary on their behalf.

Participants or the participants' parent(s)/legal guardians will be required to complete a reactogenicity e-diary through an app installed on a provisioned device or on the participant's own personal device. All participants or the participants' parent(s)/legal guardians will be asked to monitor and record local reactions, systemic events, and antipyretic medication use for 7 days from the day of administration of the study intervention. The reactogenicity e-diary allows recording of these assessments only within a fixed time window, thus providing the accurate representation of the participant's experience at that time. Data on local reactions and systemic events reported in the reactogenicity e-diary will be transferred electronically to a third-party vendor, where they will be available for review by investigators and the Pfizer clinicians at all times via an internet-based portal.

At intervals agreed to by the vendor and Pfizer, these data will be transferred electronically into Pfizer's database for analysis and reporting. These data do not need to be reported by the investigator in the CRF as AEs.

Investigators (or designee) will be required to review the reactogenicity e-diary data online at frequent intervals as part of the ongoing safety review.

The investigator or designee must obtain stop dates from the participant for any ongoing local reactions or systemic events on the last day that the reactogenicity e-diary was completed. The stop dates should be documented in the source documents and the information entered in the CRF.

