8.9.2. Visit 2 – Vaccination 2 (19 to 23 Days After Visit 1)

- Record AEs/SAEs as described in Section 8.3.
- Record details of medications currently taken and nonstudy vaccinations as described in Section 6.8.
- Perform physical examination, evaluating any clinically significant abnormalities within the following body systems: general appearance; skin; head, eyes, ears, nose, and throat; heart; lungs; abdomen; musculoskeletal; extremities; neurological; and lymph nodes.
- Measure vital signs (oral temperature, pulse rate, and seated BP (for participants ≥5 years of age). Height and weight do not need to be re-collected.
- Perform urine pregnancy test on WOCBP as described in Section 8.2.5.
- If appropriate, discuss contraceptive use as described in Section 10.3.
- Obtain a nasal swab (collected by site staff) for determination of current SARS-CoV-2 status. Please refer to the laboratory manual for further instructions.
- Review the participant's reactogenicity e-diary data. Collect stop dates of any reactogenicity e-diary events ongoing on the last day that the reactogenicity e-diary was completed and record stop dates in the CRF if required.
- Ensure and document that the participant is still eligible to continue in the study. If not, the participant may not receive further study intervention but will remain in the study to be evaluated for safety, tolerability, and immunogenicity (see Section 7.1).
- Ensure that the participant meets none of the temporary delay criteria as described in Section 5.5.
- If potential COVID-19/MIS-C symptoms are present (Section 8.11), conduct a potential COVID-19/MIS-C illness visit, including a local laboratory SARS-CoV-2 test.
- Obtain the participant's study intervention allocation using the IRT system.

- Staff member(s) will dispense/administer 1 dose of study intervention into the deltoid muscle of the (preferably) nondominant arm. Please refer to the IP manual for further instructions on this process.
- Staff must observe the participant for at least 30 minutes after study intervention administration for any acute reactions. Record any acute reactions (including time of onset) in the participant's source documents and on the AE page of the CRF, and on an SAE form as applicable.

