- The investigator or an authorized designee completes the CRFs

8.9.9. Visit 9 – 1-Month Follow-Up Visit (After Vaccination 4) (28 to 35 Days After Visit 8)

- Record AEs/SAEs as described in Section 8.3.
- Record details of medications currently taken and nonstudy vaccinations as described in Section 6.8.
- Review the participant's reactogenicity e-diary data. Collect stop dates of any reactogenicity e-diary events ongoing on the last day that the reactogenicity e-diary was completed and record stop dates in the CRF if required.
- Ensure and document that the participant is still eligible to continue in the study.
- Ensure that it is appropriate to and, if so, collect a blood sample for immunogenicity testing, dependent on participant age as referenced in Table 1 (Section 8). Please refer to the laboratory manual for further instructions. (Note: If the participant does not receive Dose 4 of BNT162b2, this blood draw is not required, and this visit may be conducted via telehealth).
- If appropriate, discuss contraceptive use as described in Section 10.3.
- Ask the participant or participant's parent(s)/legal guardian to contact the site staff or investigator immediately if any significant illness or hospitalization occurs.
- Ask the participant or participant's parent(s)/legal guardian to contact the site staff or investigator if the participant develops any symptoms as detailed in Section 8.11.
- Ask the participant or participant's parent(s)/legal guardian to contact the site staff or investigator if the participant experiences acute chest pain, shortness of breath, or palpitations (see Section 8.12).
- The investigator or appropriately qualified designee reviews COVID-19/MIS-C illness e-diary data at frequent intervals.
- Schedule an appointment for the participant for the next study visit. Remind the participant or participant's parent(s)/legal guardian to bring the reactogenicity e-diary to the next visit.

• Complete the source documents. The investigator or an authorized designee completes the CRFs.

8.9.10. Visit 10 – 6-Month Follow-Up Visit (After Vaccination 4) (175 to 189 Days After Visit 8)

- Record AEs/SAEs as described in Section 8.3.
- Record details of medications currently taken and nonstudy vaccinations as described in Section 6.8.
- Ensure and document that the participant is still eligible to continue in the study

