The duration (days) of each local reaction will be calculated as the number of days from the start of the first reported reaction to the resolution of the last reported reaction, inclusive. Resolution of the reaction is the last day on which the reaction is recorded in the e-diary or the date the reaction ends if it is unresolved during the participant e-diary recording period (end date collected on the CRF), unless chronicity is established. If there is no known end date, the duration will be considered unknown and set to missing. However, if a reaction is ongoing at the time of a subsequent dose, the end date/day for the ongoing reaction would be the date/day that the next dose is administered, which will be used for the duration computation. Participants with no reported reaction have no duration.

Onset Day

The onset day of each local reaction will be derived. Onset day is defined as the first day after vaccination that a reaction is reported of any severity.

For the onset day of each local reaction, if participants report a change in severity of the local reaction, only the first day of reporting that specific local reaction will be counted.

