6.1.2.1.2. Supplementary Analyses

To support the assessment of local reactions, the following endpoints will be summarized with the same analysis time points and analysis populations as above as well as the appropriate analysis methodology and reporting results.

PFIZER GENERAL BUSINESS

- Duration (days) of each local reaction after each dose.
- Onset day of each local reaction after each dose.

These continuous endpoints will be summarized by displaying n, mean, median, standard deviation, minimum, and maximum for each age group and disease subset.

In addition, the proportions of participants reporting each local reaction after any dose will be summarized by maximum severity level.

Figures:

Bar charts with the proportions of participants for each local reaction throughout 7 days will be plotted for each age group and disease subset. The bars will be divided into severity categories to highlight the proportions of participants by maximum severity.

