6.1.2.2.2. Supplementary Analyses

The following endpoints for assessment of systemic events will be summarized similarly to the assessment of local reactions per each age group and disease subset:

- Duration of each systemic event after each dose.
- Onset day of each systemic event after each dose.

These continuous endpoints will be summarized by displaying n, mean, median, standard deviation, minimum, and maximum for each age group and disease subset.

The use of antipyretic medication (see Section 3.1.2.3) will be summarized similarly to systemic events, except that there is no severity level associated with the use of antipyretic medication.

In addition, the proportions of participants reporting each prompted systemic event after any dose will be summarized by maximum severity level.

Figures:

Bar charts with the proportions of participants for each systemic event throughout 7 days after each dose will be plotted for each age group and disease subset. The bars will be divided into severity categories to highlight the proportions of participants by severity.

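### Reactions with no known end date drop out of the duration summaries, and those ongoing at the next dose are counted as resolved there, so mean and maximum duration can be understated

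*SAP*

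**What the plan says.** SAP 3.1.2.1 counts duration inclusively from the first reported day to resolution. There are three routes to a value.

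- **Known end.** Resolution is the last day the reaction was recorded in the e-diary or, if it was unresolved by then, the CRF date. The wording on the second case is "end date collected on the CRF), unless chronicity is established". The SAP gives no separate duration rule for chronic reactions.
- **No known end.** "If there is no known end date, the duration will be considered unknown and set to missing".
- **Ongoing at a later dose.** The next sentence provides that "if a reaction is ongoing at the time of a subsequent dose, the end date/day for the ongoing reaction would be the date/day that the" following vaccination takes place.

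SAP 3.1.2.2 derives systemic events in a similar way, and SAP 5.3 allows no further imputation. The outputs are supplementary: "Duration (days) of each local reaction after each dose" (SAP 6.1.2.1.2) and "Duration of each systemic event after each dose" (SAP 6.1.2.2.2). Each is summarised by n, mean, median, standard deviation, minimum and maximum. Neither section asks for the number of durations set to missing or ended at the next dose.

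Protocol 8.2.4 says that the investigator or designee "must obtain stop dates from the participant for any ongoing local reactions or systemic events on the last day" of e-diary completion. The visit instruction is: "Collect stop dates of any reactogenicity e-diary events ongoing on the last day that the reactogenicity e-diary was completed". It appears in Protocol 8.9.2, 8.9.4, 8.9.7 and 8.9.9, and the Schedule of Activities marks the step at Visits 2, 4, 7 and 9. Protocol 8.9.10 (Visit 10) has no such step.

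**The concern.** Whether a duration goes missing is tied to its length. A reaction that stops during the seven diary days closes itself. Only one still present when the diary ends relies on a date obtained later. Such a duration is right-censored: a lower bound is known, but the SAP discards it. A reaction ended at the next dose is also right-censored, but the SAP records it as a completed duration.

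The duration tables are the plan's summary of how long reactions last, in a population where persistence is of interest. Cells are small. SAP 2.2 gives about 1, 0, 1 and 5 adults in the four disease groups, and about 15 adolescents across three conditions. One long reaction can dominate a mean and sets the maximum.

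**Working it through.** The plan states no duration, no rate of unknown end dates and no precision for these tables, so there is no figure of its own to reproduce.

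**1. Where each rule applies.** The intervals come from the Protocol visit headings: "Visit 2 – Vaccination 2 (19 to 23 Days After Visit 1") for Dose 2, then 28 to 35 days for Dose 3 (8.9.5) and 91 to 189 days for Dose 4 (8.9.8). For a reaction starting on Day 1, assigned duration = interval + 1.

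| Reaction after | Next dose given, reaction ongoing | No later dose and no stop date |
|---|---|---|
| Dose 1 | 20-24 days, counted as resolved | missing |
| Dose 2 | 29-36 days, counted as resolved | missing |
| Dose 3 | 92-190 days, counted as resolved | missing |
| Dose 4 | cannot occur | missing |

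After Dose 4 the last scheduled stop-date step is Visit 9, at 28 to 35 days. Protocol 8.2.4 says e-diary data need not be reported as AEs, so AE follow-up need not pick up a reaction that outlasts Visit 9.

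**2. Effect in one small cell.** Assume ten reactions, nine averaging 2 days and one truly lasting T days. Mean = (9 × 2 + value used for T) / 10.

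| | T = 60 | T = 180 |
|---|---|---|
| True mean | 78/10 = 7.8 | 198/10 = 19.8 |
| Set to missing (n = 9) | 18/9 = 2.0 | 2.0 |
| Cut at 22 days (Dose 1, 21-day interval) | 40/10 = 4.0 | 4.0 |
| Cut at 29 days (Dose 2) | 47/10 = 4.7 | 4.7 |
| Cut at 92 days (Dose 3) | 7.8, no cut | 110/10 = 11.0 |

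**3. Expected effect of setting to missing.** Assume geometric durations from Day 1 with daily resolution probability p, and no next-dose rule, so this is closest to the Dose 4 case. True mean = 1/p, share beyond Day 7 = s = (1 − p)^7, mean of those = 7 + 1/p. If a fraction u of those end dates is unknown, the reported mean is [1/p − u·s·(7 + 1/p)] / (1 − u·s).

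- p = 0.50, s = 0.8%, u = 0.5: 2.00 becomes 1.97 (−1.4%).
- p = 0.35, s = 4.9%, u = 0.5: 2.86 becomes 2.68 (−6%).
- p = 0.25, s = 13.3%, u = 0.5: 4.00 becomes 3.50 (−12.5%).
- p = 0.25, u = 1: 4.00 becomes 2.92 (−27%).

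The median is unchanged (2 and 3 days) for p = 0.35 and 0.25 with half unknown. In the last case it falls from 3 to 2, because 0.4375 / 0.8665 = 0.505.

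**4. A second assumed shape.** A simulated lognormal (median parameter 1.8 days, log-SD 0.7, rounded up) has mean 2.79, with 4.2% lasting at least 7 days. Only those can lose their end date.

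| Share of those end dates unknown | Reported mean | Samples of 10 with maximum lowered |
|---|---|---|
| 5% | 2.77 | 1.7% |
| 25% | 2.72 | 8.4% |
| 100% | 2.52 | 36% |

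The median stays at 2 throughout. The maximum is never raised.

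**The case against.** A reader might infer from the missing-data sentence alone that the longest and the chronic reactions are removed at every dose, and that the reported maximum always leaves out unresolved reactions. The documents do not support that. The next SAP sentence keeps a reaction ongoing at a later dose, and such a reaction may itself be the reported maximum. A long reaction with a CRF end date is kept in full. The SAP also does not say that chronic reactions are set to missing; it leaves their handling undefined.

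Other points stand in part:

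- **Stop dates are mandatory.** They are scheduled at four visits, participants are asked to report persisting local reactions (Protocol 8.2.4.2), and ongoing reactions must be assessed at the next visit if an unscheduled one does not happen (Protocol 8.10). High shares of unknown dates therefore have no basis in the documents. This makes loss less frequent. It does not cover reactions outlasting Visit 9, or loss to follow-up.
- **Unknown does not mean long.** A reaction present on Day 7 with no stop date may have ended on Day 8 or started late in the week. That limits the size of the bias and makes its direction an expectation, not a certainty, for the mean.
- **The shortfall can be found by subtraction**, from the duration n and the reaction count for the same dose. That works for missing durations but not for those cut at the next dose.
- **Duration is supplementary in a descriptive study.** Presence and maximum severity do not use the end date, so the primary percentages are unaffected.

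**Conclusion.** The point holds as a low-priority improvement. The rule that sets durations to missing acts mainly on reactions persisting beyond Day 7, chiefly after Dose 4 or when no further dose follows. The next-dose rule shortens reactions after Doses 1 to 3 and labels them resolved, at cut-offs that differ by dose. Neither can raise the maximum, and both can be expected to lower the mean when they apply.

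The size is not computable from the documents. The assumed distributions give a fall in the mean from about 1% or less, when few end dates are unknown, to about 27% when all are unknown and durations are long. These are expected values under assumed shapes, with onset on Day 1 and no next-dose rule. They are not a bound on what one long reaction can do in a small cell, as step 2 of the working shows. The median is little affected outside the extreme case.

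**What to change.** Change both sentences in SAP 3.1.2.1, with the same effect under 3.1.2.2:

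- A reaction with no known end date is right-censored at the last date it was known to be ongoing.
- A reaction ongoing at the next dose is right-censored at that dose date.

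Changing only the first sentence would leave next-dose cut-offs analysed as true resolutions.

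In SAP 6.1.2.1.2 and 6.1.2.2.2, report for each dose the number censored for each reason. Print the maximum as at least x days when the longest duration is censored, give a Kaplan-Meier median where cell size allows, and list the censored and chronic reactions.

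The cost is a few lines of SAP text and slightly more programming, with no new data collection. Kaplan-Meier estimates assume that censoring is unrelated to the remaining duration, and they are uninformative in the smallest cells. There the counts and the listing serve instead.

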3.1.2.2. Systemic Events (Systemic Event Symptoms and Fever)

The systemic events assessed and recorded in the e-diary are fever, vomiting, diarrhea, headache, fatigue/tiredness, chills, new or worsened muscle pain, and new or worsened joint pain from Day 1 through Day 7, where Day 1 is the day of each dose. The e-diary entries from the participant and unplanned clinical assessments within 7 days after vaccination will be the primary data source for these events. In addition, any AEs recorded on the AE CRF that are considered systemic events starting within 7 days after vaccination will be consolidated with e-diary data and included in the reactogenicity report. The derivations for systemic events will be handled in a way similar to the handling of local reactions with respect to presence of event; severity level, duration, and onset day (see Section 3.1.2.1).

PFIZER GENERAL BUSINESS

The variables associated with the systemic events will be computed in a way similar to the way local reactions are computed (see Section 3.1.2.1).

The symptoms will be assessed by the participant as absent, mild, moderate, or severe according to the grading scale in Table 6. For events recorded in the AE CRF that are considered systemic events and consolidated with e-diary data, the severity will be based on the AE intensity grade recorded in the CRF.

Table 6. Systemic Event Grading Scale

	Mild (Grade 1)	Moderate (Grade 2)	Severe (Grade 3) ^a	Potentially Life-Threatening (Grade 4) ^b
Vomiting	1-2 times in 24 hours.	>2 times in 24 hours.	Requires IV hydration.	Emergency room visit or hospitalization for hypotensive shock.
Diarrhea	2 to 3 loose stools in 24 hours.	4 to 5 loose stools in 24 hours.	6 or more loose stools in 24 hours.	Emergency room visit or hospitalization for severe diarrhea.
Headache	Does not interfere with activity.	Some interference with activity.	Prevents daily routine activity.	Emergency room visit or hospitalization for severe headache.
Fatigue/tiredness	Does not interfere with activity.	Some interference with activity.	Prevents daily routine activity.	Emergency room visit or hospitalization for severe fatigue.
Chills	Does not interfere with activity.	Some interference with activity.	Prevents daily routine activity.	Emergency room visit or hospitalization for severe chills.
New or worsened muscle pain	Does not interfere with activity.	Some interference with activity.	Prevents daily routine activity.	Emergency room visit or hospitalization for severe new or worsened muscle pain.
New or worsened joint pain	Does not interfere with activity.	Some interference with activity.	Prevents daily routine activity.	Emergency room visit or hospitalization for severe new or worsened joint pain.

Abbreviation: IV = intravenous.

- a. For participants experiencing severe systemic events, a telephone contact should occur to determine if an unscheduled visit may be required.
- b. Only an investigator or qualified designee can classify a participant's systemic event as Grade 4, after clinical evaluation of the participant or documentation from another medically qualified source (eg, emergency room or hospital record). Grade 4 systemic events will be collected on the AE case report form and assessed by the investigator using the AE intensity grading scale as detailed in the protocol (Section 10.2.3).

PFIZER GENERAL BUSINESS

Oral temperature will be collected in the evening, daily, for 7 days following each dose (Days 1 through 7, where Day 1 is the day of each dose) and at any time during the 7 days that fever is suspected. Fever is defined as an oral temperature of $\geq 38.0^{\circ}$ C (100.4°F). The highest temperature for each day will be recorded in the e-diary.

Temperature will be measured and recorded to 1 decimal place. Temperatures recorded in degrees Fahrenheit will be programmatically converted to degrees Celsius for reporting. Temperatures <35.0°C and >42.0°C will be excluded from the analysis. Fever will be grouped into ranges for the analysis according to Table 7 below.

If a fever of ≥39.0°C (102.1°F) is reported in the reactogenicity e-diary, a telephone contact should occur to ascertain further details and determine whether a site visit is clinically indicated. Only an investigator or medically qualified person can confirm a participant's fever as >40.0°C (>104.0°F). If a participant experiences a confirmed fever >40.0°C (>104.0°F), the investigator must immediately notify the sponsor and, if it is determined to be related to the administration of the study intervention, further vaccinations will be discontinued in that participant. If a fever is reported in the AE CRF within 7 days after vaccination and no temperature is captured in the CRF, the fever will be included in the reactogenicity summary with "unknown" for temperature range.

Table 7. Scale for Fever

≥38.0°C to 38.4°C (100.4°F to 101.1°F)	
>38.4°C to 38.9°C (101.2°F to 102.0°F)	
>38.9°C to 40.0°C (102.1°F to 104.0°F)	
>40.0°C (>104.0°F)	

Note: Fever is defined as an oral temperature of $\geq 38.0^{\circ}$ C ($\geq 100.4^{\circ}$ F).

If a systemic event is captured in more than 1 data source, eg, e-diary, unplanned assessment, and/or the AE CRF, the highest grade (maximum severity) across all sources will be used in the summary.

3.1.2.3. Use of Antipyretic Medication

The use of antipyretic medication is also recorded in the e-diary from Day 1 through Day 7, where Day 1 is the day of each dose. For the use of antipyretic medication from Day 1 through Day 7 after each dose, the following endpoints and variables will be derived for analysis following the same rules as for local reactions (see Section 3.1.2.1), where applicable.

• Presence (yes or no) of use of antipyretic medication on each day (Day 1 through Day 7) of each dose

PFIZER GENERAL BUSINESS

- Presence (yes or no) of use of antipyretic medication on any day (Day 1 through Day 7) of each dose
- Duration (first to last day reported) of use of antipyretic medication
- Onset day of use of antipyretic medication

The use of antipyretic medication will be summarized and included in the systemic event summary tables but will not be considered a systemic event.

